13.3 Clinical Site Effect

All revascularization surgeries will be performed by experienced neurosurgeon.

14. Data Safety Monitoring Committee

A Data Safety Monitoring Board (DSMB) is composed of Academic Members, including an independent statistician, who are not otherwise participating in the trial. A DSMB charter including membership role and responsibilities will be approved by both the DSMB and the Executive Committee before the start of the trial. DSMB will meet approximately every three months to review the progress of this study (e.g. enrollment, site performance, meeting risk factor targets) as well as data on the safety of both treatment arms (e.g., side effects of RIPC) to ensure that the study meets the highest standards of ethics and patient safety. Using guidelines established by the committee and the principal investigators before the study begins, the DSMB may

recommend termination of the study if one treatment arm is found to be unequivocally more efficacious than the other or if one of the treatment arms is found to be unsafe.

Additionally, the DSMB may recommend modifications to the protocol if a reversible safety issue is identified. A letter including written recommendations and their rationale will be provided to the Chairs of the Steering Committee immediately after each DSMB meeting. This letter will be provided to the central IRBs at their request.

Committee member: [name], [name], [name]

15. Institutional Review Board/Independent Ethics Committee(IRB/IEC)

The Investigator or the Sponsor must submit this Clinical Trial Protocol to the central IRB located at Beijing Tiantan Hospital, and is required to forward to the Sponsor a copy of the written and dated approval/favorable opinion signed by the Chairman with Ethics Committee (IRB/IEC) composition.

The following information should be clearly stated on the written approval/favorable opinion: The Clinical Trial information (study number, Clinical Trial Protocol title and version number), the documents reviewed (Protocol, Informed Consent Form, Investigator's Brochure, etc.), the list of voting members along with their qualification and the date of the review.

Investigational Product will not be released at the study site and the Clinical Trial will not be initiated until a copy of this written and dated approval/favorable opinion has been received by the Sponsor.

During the Clinical Trial, any amendment or modification to the Clinical Trial

[figure not shown]
Protocol should be submitted to the Ethics Committee (IRB/IEC). It should also be informed of any event likely to affect the safety of patients or the continued conduct of the Clinical Trial, in particular any change in safety. All updates to the Investigator's Brochure will be sent to the Ethics Committee (IRB/IEC). If requested, a progress report will be sent to the Ethics Committee (IRB/IEC) annually and a summary of the Clinical Trial's outcome at the end of the Clinical Trial.

16. Safety Outcomes Assessment

The following adverse events were defined as safety outcomes: (1) elevation of plasma NSE and S-100B levels beyond normal limits after RIPC and sham RIPC procedure; (2) inability to tolerate RIPC or sham RIPC procedure that leads to the discontinuation from the study; (3) objective signs of tissue or neurovascular injury resulting from RIPC and sham RIPC procedure. An inspection that was done by staffs blinded to the study protocol included palpation of distal radial pulses, visual inspection for local edema, erythema and skin lesions, and palpation for tenderness. These safety outcomes were evaluated by observers blinded to the treatment assignment, and any suspicious adverse event associated with RIPC or sham RIPC procedure was reported to the investigators.

APPENDIXS

Study Flow Chart

Schedule of Visits and Test

	Visit 1	Visit 2	Visit 3	Visit 4	Event visit
Assessments	Screening/Randomize	At discharge	At 1 year ± 1 month	Every 12 months ±1 month	
Informed Consent	✓				
Eligibility criteria	✓				
Patient Randomization	✓				
Relevant medical history	✓				
Demographics	✓				
MRI before Surgery	✓				
CTP before Surgery	✓				
DSA before Surgery					
Vital signs	✓				✓
Modified Rankin Score	✓	✓	✓	✓	✓
MRI after surgery		✓	✓	✓	
CTP after surgery		✓	✓	✓	✓
DSA after surgery		✓	✓		✓
Current Medications	✓	✓	✓	✓	✓
Endpoints		✓	✓	✓	✓

modified Rankin Scale

The modified Rankin Scale (mRS) is a scale commonly used for measuring the degree of disability or dependence in the daily activities of individuals who have suffered a stroke, and it has become the most widely used clinical outcome measure for stroke clinical trials.

Description	Score (select one)
No symptoms at all	0 
No significant disability despite symptoms; able to carry out all usual duties and activities	1 
Slight disability; unable to carry out all previous activities, but able to look after own affairs without assistance	2 
Moderate disability; requiring some help, but able to walk without assistance	3 
Moderately severe disability; unable to walk without assistance and unable to attend to own bodily needs without assistance	4 
Severe disability; bedridden, incontinent and requiring constant nursing care and attention	5 

Dead

6

Definition of End Points

Stroke
	
Sudden symptoms and signs of focal disturbance of cerebral function associated with cerebral circulation disorders.

Ischemic stroke
	
An acute focal infarction of the brain or retina.
 
Criteria: (1) acute onset of a new focal neurological deficit with clinical or imaging evidence of infarction lasting more than 24 hours and not attributable to a non-ischemic etiology (not associated with brain infection, trauma, tumor, seizure, severe metabolic disease, or degenerative neurological disease); or (2) acute onset of a new focal neurological deficit and not attributable to a non-ischemic etiology lasting less than 24 hours, but accompanied by neuroimaging evidence of new brain infarction; or, (3) rapid worsening of an existing focal neurological deficit lasting more than 24 hours and not attributable to a non-ischemic etiology, and accompanied by new ischemic changes on brain MRI or CT, and clearly

	distinct from the index ischemic event.
Hemorrhagic stroke	An acute extravasation of blood into the brain parenchyma or subarachnoid space with associated neurological symptoms.
TIA	A neurological deficit of sudden onset, resolving completely, attributed to focal brain or retinal ischemia without evidence of associated acute focal infarction of the brain. Criteria: rapid onset of a focal neurological deficit that is without evidence of acute focal infarction of the brain, and is not attributable to a non-ischemic etiology (brain infection, trauma, tumor, seizure, severe metabolic disease, or degenerative neurological disease)
Transient neurological deficits (TNDs)	Either any reversible neurological deficit observed objectively (e.g., hemiparesis, dysarthria) or any reversible neurological deficit recognized and reported subjectively (e.g., facial palsy), without evidence of intracranial hemorrhage and cerebral

	infarction on imaging studies.
Symptomatic intracerebral hemorrhage	Any extravascular blood in the brain associated with clinical deterioration, as defined by an increase of 4 points or more in the score on the NIHSS, or that led to death and that was identified as the predominant cause of the neurologic deterioration. Intracerebral hemorrhage is defined as an acute extravasation of blood into the brain parenchyma. Criteria: evidence of hemorrhage in the brain parenchyma demonstrated by head imaging, surgery, or autopsy
Asymptomatic intracerebral hemorrhage	an acute extravasation of blood into the brain parenchyma without clinical deterioration. Criteria: evidence of hemorrhage in the brain parenchyma demonstrated by head imaging, surgery or autopsy
Other symptomatic intracranial hemorrhage	Any extravascular blood within the cranium associated with clinical deterioration, as defined by an increase of 4 points or more in the score on

	
the NIHSS, or that led to death and that was identified as the predominant cause of the neurologic deterioration. Other Intracranial Hemorrhage is defined as an acute extravasation of blood into the subarachnoid space, epidural space, or subdural space with associated symptoms. Criteria: evidence of hemorrhage in the subarachnoid space, epidural space, or subdural space demonstrated by head imaging, surgery, or autopsy

Other Asymptomatic intracranial hemorrhage
	
An acute extravasation of blood into the subarachnoid space, epidural space, or subdural space without associated symptoms. Criteria: evidence of hemorrhage in the subarachnoid space, epidural space, or subdural space demonstrated by head imaging, surgery, or autopsy

Ischemic vascular death
	
Death due to ischemic stroke, myocardial infarction, sudden cardiac death, arrhythmia, pulmonary embolism, bowel or limb infarction, or

	any death not readily attributable to a non- ischemic cause
Hemorrhagic Vascular death	Death due to intracranial or systemic hemorrhage
Dependent	Unable to look after own affairs without assistance, mRS score > 2

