Secondary endpoint	
 • The severity of the ischemic stroke after surgery • Number of patients occurred restroke at Follow-up Period • Number of patients dependent or death at follow-up period • Number of patients with improved neurological function at follow-up period • Perfusion status of patients at follow-up period • Number of patients with any side effects of remote ischemic preconditioning (RIPC) treatment.
Inclusion Criteria	
 • Patients who diagnosed with moyamoya disease • Adults 18 to 65 years of age • The onset symptoms manifested as ischemic symptoms (TIA or stroke) or atypical symptoms (headache, epilepsy or asymptomatic) • Able to receive the necessary imaging examination • Patients who pre-agreed to the study
Exclusion Criteria	
 • Prior cerebral hemorrhage history • Other brain or cerebrovascular disease • Previous history of revascularization surgery • Dependent (mRS > 2) • Receive other type of revascularization surgery • Peripheral blood vessel disease (especially subclavian arterial and upper limb artery stenosis or occlusion).

	
 • Patients who do not agree with the study
Sample Size	
Sample size and power were calculated based on previous studies and postoperative neurological complications, which were much better to indicate the efficacy of RIPC. We calculated the simple size and power with PASS, version 11 (NCSS, LLC, Kaysville, UT, USA). We expected ≈10% of subjects in the RIPC group and 20% of subjects in the other 2 groups would have new postoperative neurological complications. The intended target sample size was 328 subjects allowing 15% loss to follow-up and with 90% power and an α of 0.05 (2-sided) of significance.

Follow-up	
The face-to-face interview will be performed by study neurologists at discharge, at 6 months and at 12 months (or by telephone) after the recruitment of patients.

2. Study Rationale

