
4. Study Plan and Procedure

Study Design and Flow Chart

This study was a multi-center, prospective, randomized, controlled trial of

randomized (1:1) adult ischemic MMD patients undergoing indirect revascularization into two groups:

1. RIPC group

Remote limb ischemic preconditioning (RIPC) is consisted of five 5-min cycles of bilateral arm ischemia/reperfusion, it is induced by a sphygmomanometer placed on bilateral arm and inflated to 200 mmHg for 5-min followed by deflating the cuff for 5-min, patients in the RIPC group will do it twice a day for at least five days before EDAS.

2. sham RIPC group

Sham RIPC group is consisted of five 5-min cycles of bilateral arm ischemia/reperfusion, induced by a sphygmomanometer placed on bilateral arm and inflated to 60 mmHg for 5-min followed by deflating the cuff for 5-min, they will do it twice a day for at least five days before EDAS.

5. Study Endpoints

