6.2 Exclusion Criteria

- Prior cerebral hemorrhage history
- Other brain or cerebrovascular disease
- Previous history of revascularization surgery
- Dependent (mRS > 2)
- Receive other type of revascularization surgery

- Peripheral blood vessel disease (especially subclavian arterial and upper limb artery stenosis or occlusion).
- Patients who do not agree with the study

7. Informed Consent

The principles of Informed Consent, according to FDA Regulations and ICH guidelines on GCP, will be followed. Investigator will submit a copy of the proposed consent form, together with the study protocol, to the central Institutional Review Board (IRB) at Beijing Tiantan Hospital for approval. Each eligible patient who wishes to participate in this study will be invited to give written informed consent. Before the consent is signed, a trained researcher will explain study purpose, description, duration, potential risks and anticipated benefits, cost and compensation, voluntary nature of participation, appropriate alternatives, treatment for study-related injury, whom to contact with questions or concerns or study-related injuries, maintenance of confidentiality of record, and funding source. Patients will be encouraged to consent for the blood drawing for biomarker testing only if they would be prepared to enroll in the trial.

8. Enrollment of Patients

All patients with moyamoya disease who visit the research center will be asked if they are involved in the study as long as they meet the inclusion criteria. This study is included in patients who have voluntarily participated in the study and signed

informed consent and did not meet the exclusion criteria.

9. Randomization of Patients

Patients was randomized by random number table

10. Image Data Evaluation

In this study, Suzuki staging was determined by DSA technique; subarachnoid hemorrhage, ischemic stroke (cerebral infarction), and cerebral hemorrhage were diagnosed using the Fourth National Conference on Cerebrovascular Diseases (1995).

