In order to prevent errors in the research due to the interpretation technique, this study set up a decision-making committee to uniformly judge the imaging data of the patients enrolled. Two experienced neuroimaging physicians conducted mutual blind interpretation, and the results of the inconsistent report should be ranked third. The senior neuroimaging chief physician will conduct a trial and finally submit true and reliable imaging results for all cases. The interpreter does not participate in the study design and does not know the patient's clinical information.

11. Bio sample test

Blood samples were drawn from the cubital vein; the points of measurement included baseline, pre-EDAS, right 1 hour and 24 hours post-EDAS. The collected blood samples were sent for examination, and plasma neuron specific enolase (NSE) and human S protein 100B (S-100B) levels were examined in the test samples.

11. Schedule of Follow-up and Post-study Follow-up Period

All patients will be followed up until the primary endpoint or the end of the trial.

Complete endpoint information will be obtained with the best effort irrespective of patient study status, unless patients withdraw consent to participate the trial. The face-to-face interview will be performed by study neurologists at discharge, at 6 months and at 12 months (or by telephone) after the recruitment of patients.

Visits	Windows	Definition
Randomization	0 day	Study Day 0 day
At discharge	0 day	Based on the number of hospitalization days
At 6 months	14 days	Day 166-194
At 12 months	30 days	Day 330-390

12. Quality Assurance

Periodic monitoring and auditing will be performed at each site to ensure that data generated during the study reflect what is specified in the protocol, and data consistence by comparing data in the case report form (CRF) and data collected in source documents for (CRF vs. source documents). If patients who have events go to non-study sites for treatment, source documents will be photocopied for review. It should be guaranteed that the study investigators and relevant study personnel are available during the monitoring visits and possible audits.

13. Statistical Consideration

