13.1 Sample size estimates

This study was a cohort study of prospective, multicenter, hospital-based, continuous enrollment patients. It is planned to choose three hospitals in Beijing. The investigation and registration of the ending events are carried out through hospital follow-up examinations, investigations, registration and hotline reports, face-to-face or telephone follow-up, and monitoring information database supplementation.

Sample size and power were calculated based on previous studies and postoperative neurological complications, which were much better to indicate the efficacy of RIPC.

We calculated the simple size and power with PASS, version 11 (NCSS, LLC, Kaysville, UT, USA). We expected $\approx 10\%$ of subjects in the RIPC group and 20% of subjects in the other 2 groups would have new postoperative neurological complications. The intended target sample size was 328 subjects allowing 15% loss to follow-up and with 90% power and an α of 0.05 (2-sided) of significance.

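### Section 16 ties cuff intolerance to leaving the study, Section 11 wants endpoints regardless, and Section 13.2 never says that all randomised patients are analysed as allocated

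*Combined protocol and SAP*

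**What the plan says.** Four places bear on who enters the primary comparison.

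- **Section 16 (Safety Outcomes Assessment)** counts as its second safety outcome "inability to tolerate RIPC or sham RIPC procedure that leads to the discontinuation from the study". The wording refers to the study, not to the cuff sessions.
- **Section 11 (Schedule of Follow-up)** says: "Complete endpoint information will be obtained with the best effort irrespective of patient study status, unless patients withdraw consent". This governs data collection.
- **Section 13.2 (Statistical Analyses)** names the Pearson chi-square test for categorical outcomes. It defines no analysis population and no rule for missing outcomes, for patients never operated on, or for patients given a different operation.
- **Section 6.2 (Exclusion Criteria)** lists "Receive other type of revascularization surgery" with no time point, next to a separate exclusion for earlier revascularization.

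On timing, the Appendix visit schedule puts randomisation at Visit 1 with screening and ticks eligibility only there. Section 4 then has at least five days of cuff sessions before EDAS, at 200 mmHg (RIPC) or 60 mmHg (sham). Section 5.1 counts the primary endpoint over 30 days from surgery.

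**The concern.** Intolerance can only appear once cuff sessions have begun, so it is always a post-randomisation event. The arms differ only in cuff pressure, and more intolerance at 200 than at 60 mmHg is a reasonable expectation. If intolerant patients are treated as having left the study and do not reach the chi-square table, each arm loses a different number, and possibly a different kind, of patient. What remains is no longer the randomised comparison.

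Sections 16 and 11 pull in different directions, and Section 13.2, which should settle the matter, is silent. Even if Section 11 is followed fully, endpoint data could be collected and the patient still left out of the primary analysis. The choice could then be made after the results are known.

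**Working it through.** **What the plan gives.** The plan gives no intolerance rate and no event risk for intolerant patients, so it has no figure of its own to reproduce on this point. It supplies only the setting:

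- Two arms: "randomized (1:1) adult ischemic MMD patients undergoing indirect" revascularization (Section 4).
- Total size: "The intended target sample size was 328 subjects allowing 15% loss to follow-up and with 90% power" (Section 13.1), hence 328/2 = 164 per arm.
- Control risk: "20% of subjects in the other 2 groups would have new postoperative neurological complications" (Section 13.1).
- Test level: "an α of 0.05 (2-sided) of significance", so the nominal chance of a false finding in favour of RIPC is 2.5%.

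The 328 does not itself follow from the stated inputs. For 10% vs 20% at 90% power, the usual formula gives 266 per arm, 532 in total before loss. That is a separate matter, and 164 per arm serves here only as the planned arm size.

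**Assumptions (mine).** There is no true effect, with 20% risk in both arms. A fraction d of an arm is dropped, with d = 0.10 for RIPC and 0.02 for sham. Dropped patients have risk r, from 10% to 40%. Every dropped patient is missing from the analysis.

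**Risk among those retained:** q = (0.20 − d·r)/(1 − d).

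For r = 0.40:
- RIPC: (0.20 − 0.10×0.40)/0.90 = 0.1778
- sham: (0.20 − 0.02×0.40)/0.98 = 0.1959
- difference D = −0.0181

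**False-benefit rate:** Φ[(−1.96·s0 − D)/s1], where s0 and s1 are the pooled and unpooled standard errors. Retained numbers are 164×0.90 = 147.6 and 164×0.98 = 160.7. For r = 0.40, s0 = 0.0445 and s1 = 0.0444, giving Φ(−1.555) = 0.060.

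| Risk in dropped patients | RIPC retained | Sham retained | Spurious difference | False benefit (nominal 2.5%) |
|---|---|---|---|---|
| 10% | 21.1% | 20.2% | 0.9 points against RIPC | 1.6% |
| 20% | 20.0% | 20.0% | none | 2.5% |
| 30% | 18.9% | 19.8% | 0.9 points for RIPC | 3.9% |
| 40% | 17.8% | 19.6% | 1.8 points for RIPC | 6.0% |

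**Sensitivity to the drop rate, at 40% risk.** With 5% vs 2% dropped, the spurious benefit is 0.6 points (3.5% false benefit). With 15% vs 2% it is 3.1 points (about 10%).

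**Patients involved.** At 10% vs 2%, 164×0.10 + 164×0.02 = 19.7, about 20 of 328 (6%).

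**The other operation.** There is nothing to compute, because no rate is given and cuff pressure has no stated link to the choice of operation.

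**The case against.** The strongest reply is that the plan already protects against this. Section 11 commits to collecting endpoints whatever the study status, with withdrawn consent as the only exception. The Section 16 phrase is one item in a list of safety outcomes; it labels an event to be counted and orders nobody's removal. That is fair, and it rules out the reading that the plan drops intolerant patients as a rule. It does not settle who is analysed: Section 11 concerns collection, is best effort, and is not echoed in Section 13.2.

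A reader might also infer that a patient who stops the cuff before surgery has no primary outcome. The documents do not support this. Nothing says that stopping the cuff cancels EDAS, and a patient who goes on to surgery has an ordinary 30-day window. Only a patient who is never operated on has no window.

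A reader might likewise take the other-operation exclusion as a second route out after randomisation. Its place beside the exclusion for earlier surgery shows that it concerns the current operation, but not when it is applied. Eligibility is ticked only at Visit 1, so a screening reading is at least as natural. Nothing suggests that it would differ by arm.

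Finally, the 6.0% figure needs high-risk patients to be the ones who stop, and all of them to be dropped. The loss of about 20 patients lies within the plan's 15% allowance. Both points stand. The allowance, however, protects numbers; it does not protect against unequal, selective loss.

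**Conclusion.** The point holds as an unresolved inconsistency plus a missing analysis set. Sections 16 and 11 need reconciling, and Section 13.2 must say that the primary comparison keeps all randomised patients in their allocated arm.

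The size is unknown. With 10% vs 2% dropped, the illustration runs from 0.9 points against RIPC to 1.8 points in its favour as the risk in dropped patients goes from 10% to 40%, with no bias at 20%. It rests on assumed drop rates, assumed risks and complete exclusion of those who stop. It should not be read as showing that the plan favours RIPC: the direction cannot be known beforehand, which is the reason to fix the population in advance.

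The other-operation exclusion is ambiguous in timing only; no difference between arms can be claimed for it.

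**What to change.** - **Section 16, reconciled with Section 11:** record intolerance as stopping the cuff sessions, with the patient kept in follow-up and in the analysis. When sessions should stop remains a clinical decision.
- **Section 13.2:** define the primary comparison as all randomised patients by allocated arm, including those who stop the cuff or receive another operation. State how patients never operated on are counted, since their 30-day window does not start. Add a sensitivity analysis for missing outcomes, and a per-protocol analysis as supportive only.
- **Section 6.2 and the synopsis:** word the exclusion as another type of revascularization planned at screening.

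**Cost.** These are wording changes and two extra analyses, with no new visits. The statistical price is dilution from incomplete conditioning. If a fraction f of the RIPC arm gets no benefit, its expected rate becomes 0.10 + f×0.10. For f of 5% to 15% (assumed), that is 10.5% to 11.5%. Power with 164 per arm then falls from 72% to between 67% and 56%. That loss should be faced in the sample size, not avoided by dropping patients.
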